This project will develop and pilot test a new smartphone-based system for AUD patients, their partners, and clinicians called PartnerCHESS. PartnerCHESS will integrate key features of ABCT and A-CHESS. The project has three specific aims:

1. Integrate A-CHESS with key features of ABCT to create PartnerCHESS to serve patients, partners, and clinicians.
2. Conduct a pilot test (a small randomized clinical trial) of PartnerCHESS to estimate effect size and refine the protocol, procedures, recruitment strategy, measurements, and operations we would use in a large RCT.
- 3a. Decide whether to pursue an R01 application, and if so, 3b. plan for the R01.

The project would engage 6 couples to help design PartnerCHESS, test its usability and give feedback on its utility. Once ready, the system would be tested by 34 other couples randomized to receive either PartnerCHESS + treatment as usual (TAU) or A-CHESS + TAU for a 6-month trial. We will collect survey data at baseline, 2, 4, and 6 months and analyze it to see if a large clinical trial holds promise and, if so, produce an application to support a full-scale trial based on the technology developed and the research procedures employed in the pilot test.

The study is important to public health because of the scope of the alcohol abuse and the potential of technology to improve the lives of both patients and partners. If successful, such technology could greatly broaden the reach and impact of AUD treatment in general and couples therapy in particular.

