Data analysis plan. The analysis will: (1) determine if there is a significant difference between study arms over the 6-month pilot test, and (2) explore the conceptual model (Figure 1)—i.e., the relationships between the primary and secondary outcomes and patient and partner mediators, moderators, the 2 study arms, and covariates. We will report descriptive statistics for all demographic and clinical variables in both arms to ensure that randomization produced demographically and clinically comparable groups; if not, variables with significant differences will be included as covariates in a sensitivity analysis. Analysis of the impact of PartnerCHESS+TAU vs. A-CHESS+TAU will focus on outcomes over time computed from data at pretest, 2, 4, and 6 months, with separate models for the primary outcomes and each secondary outcome. Linear mixed effects models—which account for dependence among successive observations on the same patient and incomplete data—will analyze outcomes longitudinally and at each time point. Initial intercepts will be modeled as random variables to provide variance and covariance estimates of intervention effects at each time point and across and between patients. A generalized linear mixed effects model, based on a multiple regression, will be used for the continuous outcome of risky drinking days.⁸⁹ We will conduct specific treatment time contrasts both between and within groups to test time-based effects. Sensitivity analyses (with and without covariate adjustment) will determine the robustness of covariate-related error control.

Modeling mediation and moderation. For both patients and partners, we will test the effect of the interventions on potential mediators (competence, intrinsic motivation, and relatedness) on primary and secondary outcomes, using Barron and Kenny's⁹⁰ steps: Step 1, the outcomes (e.g., risky drinking days) will be regressed on the interventions (arm 1 vs. arm 2); Step 2, mediators will be regressed on the interventions; Step 3, the intervention variable and mediator variables will be regressed on the outcomes.

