Mediator effects are statistically significant if: (a) the beta-weight coefficients in Steps 1 and 2 differ significantly from zero, (b) the Step 3 beta-weight coefficient of the mediators is statistically significant, and, (c) the difference between the beta-weight coefficients of the intervention variable in Steps 1 and 3 is statistically greater than zero. We will test whether patient and partner gender moderates the effect of intervention on outcomes. We will derive interaction terms for the predictor variables, incorporating them into the regression model, and determine whether those terms significantly contribute to the outcome predictions that exist independent of other significant contributors. We will examine moderated mediation because the process may be more complex than can be rendered by treating the factors independently (e.g., a mediator may be stronger for women than men or vice versa). We will develop a moderated mediation structure to determine whether the results are best described by meaningful higher-order interaction terms based on mediator-moderator combinations.

Power. We understand that estimating effect size from pilots can lead to bad estimates. A paper by Leon, Davis, and Kraemer² points out that a pilot study can evaluate the. It informs feasibility and identifies modifications needed before a larger hypothesis-testing study. But (they argue) a pilot study does not provide meaningful effect size estimates for planning subsequent studies because of the imprecision inherent small samples. Rather, a hypothesis-testing study should be designed to detect the smallest difference that is generally agreed to be clinically meaningful. Several studies (e.g. Walters et al.)³ suggest that an effect size of $d=.35$

is considered clinically meaningful. So we will use $d=.35$ at a power of .85 to determine sample size needed for the large study.

This particular pilot is not powered to detect any effect on outcomes. Once the R34 analyses are complete, we will develop the R01 proposal based on the previous work mentioned above but also considering what we learn about the feasibility of recruitment, randomization, retention, assessment procedures, and new methods mentioned above.

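### The mediation steps leave out the month-0 mediator and outcome, so the Step 3 mediator coefficient includes person-to-person correlation that existed before the intervention

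*Combined protocol and SAP*

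**What the plan says.** Section 8.0, under Modeling mediation and moderation, tests "potential mediators (competence, intrinsic motivation, and relatedness) on primary and secondary outcomes", for patients and for partners, in three regressions. Step 1 relates the outcome to arm alone. The second is "Step 2, mediators will be regressed on the interventions". The third is "Step 3, the intervention variable and mediator variables will be regressed on the outcomes"; read literally this reverses the regression, but the intended model is clearly outcome on arm plus mediators. No step names a covariate, a baseline value or a time point.

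A mediator is credited only if all three of these hold:

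- (a) "the beta-weight coefficients in Steps 1 and 2 differ significantly from zero"
- (b) "the Step 3 beta-weight coefficient of the mediators is statistically significant"
- (c) "the difference between the beta-weight coefficients of the intervention variable in Steps 1 and 3 is statistically greater than zero"

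On data, the project summary states "We will collect survey data at baseline, 2, 4, and 6 months". Table 2 (Section 6.0) gives months 0, 2, 4 and 6 for every mediator and for both primary outcomes. Its covariate block has a row for the baseline of the outcomes and none for the baseline of the mediators. The sentence promising analyses with and without covariates belongs to the arm-comparison paragraph (Data analysis plan), not to the mediation steps.

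**The concern.** Randomisation protects the arm comparisons in Steps 1 and 2. It does not protect the mediator-outcome comparison in Step 3, because nobody is randomised to a level of competence, motivation or relatedness. If patients more committed to sobriety already drink less at enrolment, that difference persists at follow-up and appears in the Step 3 mediator coefficient, even when a change in commitment does nothing to drinking. Criterion (c) is not independent protection. When arm moves the mediator, a spurious mediator coefficient also pulls down the arm coefficient.

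The pilot's mediation results have a use. Section 2.0 says the project is meant to finalise the analytical protocol for a later R01. Section 6.0 says the survey will be trimmed while keeping what the conceptual model needs. A biased Step 3 could affect both.

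**Working it through.** **The plan's own figure.** The only sample-size arithmetic given is completers per arm (Section 5.0): 34/2 × (1 − 0.10) = 15.3, which matches the stated figure of about 15.

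**Assumptions not in the documents.** Two-sided alpha .05; one follow-up value per person; normally distributed scores with unit variance, analysed by least squares; a stable trait making up 0.5, 0.6 or 0.7 of the variance of mediator and outcome; trait correlations of 0.5, 0.6 or 0.7. The pre-existing mediator-outcome correlation is the product, r = .25, .36 or .49. The true mediator-to-outcome effect is zero throughout. Criterion (c) is tested with a one-sided Sobel z.

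**Check by hand.** With unit variances, the Step 3 mediator slope as written equals r although the causal effect is 0. With 30 people and 27 residual degrees of freedom, its expected t is about r√27/√(1 − r²):

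- r = .25: 1.34
- r = .36: 2.01
- r = .49: 2.92

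Against a critical value of 2.05 these imply rejection in roughly 24%, 48% and 81%. The spurious drop in the arm coefficient is (arm effect on mediator) × r. At 0.8 SD it is 0.8 × .25 = 0.20, 0.8 × .36 = 0.29 and 0.8 × .49 = 0.39 SD.

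**Simulation, 15 per arm, arm moves mediator and outcome by 0.8 SD each:**

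| | r = .25 | r = .36 | r = .49 |
|---|---|---|---|
| Step 3 rejects, as written | 26% | 49% | 79% |
| Step 3, month-0 outcome only added | 12% | 17% | 22% |
| Step 3, both month-0 values added | 7% | 8% | 9% |
| Full rule (a)-(c), as written | 8% | 16% | 29% |
| Full rule, both month-0 values added | 2% | 4% | 5% |

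With no stable correlation Step 3 rejects 5%, so the excess comes from that correlation. Repeat runs, with r = .42 added (64% as written), give 6-11% for adjusted Step 3, and 7-30% as written against 2-6% adjusted for the full rule.

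**Full rule as written, smaller arm effects, 15 per arm.** The expected Step 1 t is d√(15/2). For d = 0.35 this is 0.96 and for d = 0.8 it is 2.19, against 2.05. Criterion (a) therefore blocks most false credit at the smaller effect.

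- Arm moves both by 0.35 SD: about 1-4% (1.4% at r = .36).
- Arm moves the mediator by 0.8 SD but not the outcome: about 1-2%.

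**Reuse in a large trial.** The Power paragraph names d = .35 at power .85. At alpha .05 this needs 2(1.960 + 1.0364)²/0.35² = 146.6, so 147 per arm; 150 was simulated. With 0.35 SD on both and r = .36, the full rule falsely credits the mediator in about 75% as written and about 40% with both month-0 values.

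**Limits of adjustment.** If month-0 scores capture the stable part without error (month-0 correlation .6, stability .7), adjustment brings Step 3 from 35% to 5% at 15 per arm and from 100% to 5% at 150. With the noisy baselines assumed above (r = .36), adjusted Step 3 still rejects about 45% at 150 per arm. If a shared cause arising after baseline is added (30% of the non-stable variance), it rejects 34% at 15 per arm and 100% at 150.

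**Precision.** A baseline with stability s shrinks the residual SD by √(1 − s²): 0.87 at s = 0.5 and 0.71 at s = 0.7. After the lost degrees of freedom, the arm-effect standard error in Steps 1-2 is about 11-28% smaller.

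**The case against.** The tempting stronger reading is that the plan would wrongly declare mediation in a quarter to four-fifths of pilots. The documents do not support it. Those rates are criterion (b) alone, and the plan also requires significant Steps 1 and 2 and a significant drop in the arm coefficient. At 0.35 SD, the only effect size the plan names (and it names it for the later trial), false credit at pilot size stays below 5%. The comparator is an active app, so 0.8 SD on both variables is a demanding scenario. This stands and limits the size of the point.

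The plan also describes this work as exploring a conceptual model, says the pilot is not powered for outcomes, and makes mediation no go/no-go criterion. That stands too. It lowers the stakes but leaves the Step 3 estimates biased.

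It can be said that covariates are already provided for. That stands only in part. The baseline outcome is listed but not tied to Steps 1-3, and on its own it leaves Step 3 at 12-22%. Month-0 mediators are listed nowhere. The covariates promised for the arm comparison address imbalance between arms, whereas this confounding is present with perfectly balanced arms. The random intercepts in the arm-comparison models would not by themselves separate within-person from between-person association, even if carried over.

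Finally, the plan names no time point, so the use of follow-up values is inferred. Including month 0 among the analysed values would bring the pre-intervention association in directly.

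**Conclusion.** The point holds as a specification gap in an exploratory analysis. Steps 1-3 omit month-0 values already being collected, and the Step 3 coefficient is biased by stable correlation between mediator and outcome. At pilot size the consequence is mainly for the Step 3 estimates and for what is concluded about the conceptual model. A false declaration under the full rule becomes common only if arm truly moves both mediator and outcome by a large amount, or if the rule is carried into a trial of about 150 per arm.

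A reader might also infer that baseline adjustment makes Step 3 a valid causal test. It does not: it reduces the confounding and leaves some behind. All the rates rest on assumed correlations, stabilities, arm effects and alpha, and on normal scores standing in for counts of days. The direction of the bias in Step 3 does not depend on the exact values chosen, but its size does.

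**What to change.** In the mediation paragraph of Section 8.0:

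- Steps 1 and 2: add the month-0 outcome and the month-0 mediator as covariates beside arm.
- Step 3: regress the follow-up outcome on arm, follow-up mediator, month-0 mediator and month-0 outcome. This also corrects the reversed wording.
- State which follow-up time points supply the mediator and the outcome.
- State that the remaining mediator-outcome association is observational.
- In Table 2, add the baseline of the mediators to the covariates.

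The cost is SAP wording and two degrees of freedom per model; no new data are needed. Under the assumed stabilities of 0.5-0.7, the more precise arm estimates in Steps 1-2 outweigh that loss.

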5.0 TREATMENT PLAN

This project includes a 15-month initial development phase that will involve 6 dyads and a small 6-month randomized trial that will involve 34 dyads. During the 6-month randomized trial half the dyads will use A-CHESS and half will use PartnerCHESS. During that time, the smartphone will continuously collect data on how patients, partners, and clinicians are using the technologies, along with responses to a weekly survey about their satisfaction with services and suggestions for improvement. We will also conduct surveys with participants at baseline and at 2, 4 and 6 months. Based on past CHESS research, we expect a dropout rate of about 10%, leaving about 15 dyads per arm to complete the pilot RCT.

Initial development phase. After recruitment and consent, 6 dyads will take part in 3 2-hour focus groups to help develop and test the PartnerCHESS app. Topics for the 3 focus groups include:

- Initial design feedback
- Mock-ups feedback
- Content feedback
- Usability testing
- Pilot testing
- Review and give feedback on surveys to be used during the pilot

During the development phase the PartnerCHESS software design team will develop a series of interface prototypes and use rapid-cycle testing to gather user feedback about them. We will ask questions such as how intuitive the system is (Can people find what they are looking for? Do the graphics and naming conventions make sense?), how visually appealing it is, and whether the services seem useful. We will use tools such as wireframes, mockups, and paper and html prototypes to test prototypes, use feedback to quickly make changes, and test again. The information gathered from the 6 dyads will help us gauge ease of use, perceived value and reveal other changes to make before the pilot test begins. Our baseline and follow-up surveys will also be tested with the 6 dyads. Study participants will receive \$35 for each focus group they attend for a maximum of \$105.

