Concurrent Tx services received	Patient	TSR	McLellan et al. ⁸⁶	6	0, 2, 4, 6
Addiction severity	Patient	DSM-5	APA ⁸⁷	11	0, 2, 4, 6
Addiction treatment level (e.g. IOP)	Patient	Administrative records	Collins et al. ⁷⁵	11	0, 2, 4, 6

Items were selected based on the conceptual model (Figure 1). When possible, we will use questions from PhenX toolkit on SUD so that results are comparable to those in other studies.⁸⁸ The survey will have 134 questions for partners and 130 for patients. Using the survey in this pilot will help us determine which items can be eliminated or altered to reduce participant burden while obtaining the data necessary to analyze our conceptual model. All measures have been validated in the empirical studies referenced above.

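### A mediator can be called significant only if the total arm effect is significant too, in a pilot not powered for that effect, so a negative mediation verdict is weak evidence

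*Combined protocol and SAP*

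**What the plan says.** Section 8.0, under modeling mediation and moderation, follows the Baron and Kenny steps. Step 1 regresses the outcome on arm, Step 2 regresses the mediator on arm, and Step 3 puts arm and mediators in one model for the outcome. The decision rule has three conditions joined by 'and'. The first is "Mediator effects are statistically significant if: (a) the beta-weight coefficients in Steps 1 and 2 differ significantly from zero". The second is a significant mediator coefficient in Step 3. The third is "c) the difference between the beta-weight coefficients of the intervention variable in Steps 1 and 3 is statistically greater than zero".

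The Power paragraph of the same section states: "This particular pilot is not powered to detect any effect on outcomes". Section 5.0 gives the expected numbers: "we expect a dropout rate of about 10%, leaving about 15 dyads per arm to complete the pilot RCT". Exploring the conceptual model is the second of two analysis goals in section 8.0, and the linear mixed models "will analyze outcomes longitudinally and at each time point". The section states no alpha, names no test for the third condition, and describes no interval for an indirect effect.

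**The concern.** A verdict that requires Step 1 cannot be positive more often than Step 1 passes, however strong the path through the mediator is. The plan thus makes its mediation answer depend on the one test that it says it cannot rely on. Two things follow. Real mediators will usually be labelled not significant, and the few that pass will tend to do so with exaggerated estimates, because passing needs a large observed arm effect.

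Steps 2 and 3 may still be computed when Step 1 fails. What is missing is a commitment to report the indirect effect, with an interval, in that case. The practical stake is the second analysis goal. Section 6.0 also gives the questionnaire a further purpose: "help us determine which items can be eliminated or altered to reduce participant burden while obtaining the data necessary to analyze our conceptual model". A label of not significant that is nearly as likely with a real mediator as without one would be a poor guide to that choice.

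**Working it through.** **Completers.** 34 dyads randomized 1:1, about 10% dropout: 34 × 0.90 / 2 = 15.3 per arm, which reproduces the plan's figure of about 15.

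**Step 1 power.** Input d = 0.35, the value section 8.0 calls clinically meaningful and uses to size the later large trial. Alpha 0.05 two-sided is assumed. For a two-sample t-test the noncentrality is d × √(n/2).
- n = 15: 0.35 × √7.5 = 0.96, df 28, power 15.3%.
- n = 17 (no dropout): 0.35 × √8.5 = 1.02, df 32, power 16.8%.

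This is the ceiling on a positive mediation verdict in a simple comparison.

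**The full rule.** Simulation with 20,000 trials per case: 15 per arm, one mediator, normal outcome, within-arm SD 1, one unadjusted follow-up, total d = 0.35. Path sizes are assumptions. Steps 1, 2 and 3 are each tested at p < 0.05 two-sided. The third condition is tested by a delta-method z, above 1.645 (one-sided) or 1.96 (two-sided), because the plan names no test. Each pair below is one-sided / two-sided.

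| Arm→mediator × mediator→outcome (+ direct) | Full rule | Step 1 condition removed | Mean estimate when rule is met (true value) |
|---|---|---|---|
| 0.7 × 0.5 | 8.7 / 6.2% | 34.5 / 21.8% | 0.59 / 0.66 (0.35) |
| 1.0 × 0.35 | 5.5 / 3.7% | 32.7 / 19.4% | 0.61 / 0.69 (0.35) |
| 0.5 × 0.5 + 0.10 | 6.3 / 3.9% | 19.7 / 11.3% | 0.55 / 0.63 (0.25) |

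**Effect of the Step 1 condition alone.** Sample size is the same in both columns. The ratio runs from 11.3 / 3.9 = 2.9 to 32.7 / 5.5 = 5.9, so the condition cuts detection about three- to six-fold.

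**Exaggeration.** From 0.59 / 0.35 = 1.7 to 0.63 / 0.25 = 2.5 times the truth. Over all trials, without the condition, the estimate averages the true 0.35 or 0.25.

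**What each verdict is worth.** With no mediator (either path zero, total d still 0.35) the rule is met in 0.0–0.9% of trials.
- Negative: from 91.3 / 100 = 0.91 to 96.3 / 99.1 = 0.97 times as likely with a real mediator as without one.
- Positive: 5.5 / 0.9 = 6.1 times as likely in the weakest case, hence roughly 6 or more.

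**A more favourable setting.** The plan also analyzes outcomes longitudinally. Take the baseline-adjusted mean of three follow-ups with complete data and an assumed correlation ρ of 0.3 to 0.7. The variance factor is (1 + 2ρ)/3 − ρ². In simulation (10,000 trials per case) Step 1 then passes in 27–38% of trials, the full rule in 9–27%, and the rule without Step 1 in 23–69%. The gap narrows but stays.

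**The case against.** *The sample size is the real cause, and the plan admits it.* Largely true. Without the Step 1 condition, 65–89% of real mediators are still missed with one follow-up (100 − 34.5 to 100 − 11.3). A reader might infer that the rule explains the whole miss rate; it does not. It is an avoidable loss on top of a small sample.

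*The indirect effect is already in the plan.* Partly true. A reader might infer that no indirect effect will be estimated at all. The text does not support that: nothing stops Steps 2 and 3 if Step 1 fails, and the third condition needs the change in the arm coefficient. With one mediator in a linear model, that change is the indirect effect. If several mediators enter Step 3 together, as its plural wording allows, the change is the sum of their indirect effects. The gap is therefore the interval and the commitment to report.

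*Nothing depends on the verdict.* This stands. A reader might infer that item deletion or the R01 decision will be misled. Section 6.0 does not tie item choice to mediation verdicts, and section 8.0 bases the R01 on previous work and what is learned about feasibility.

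*The figures rest on assumed paths and normal outcomes.* This stands too. The plan says: "A generalized linear mixed effects model, based on a multiple regression, will be used for the continuous outcome of risky drinking days". The percentages do not cover that model.

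**Conclusion.** The point holds. As written, a mediator can be declared significant only when the total arm effect is, in a pilot that section 8.0 says is not powered for any outcome effect. With one mediator, a normal outcome, one unadjusted follow-up, total d = 0.35, alpha 0.05, 15 per arm and the assumed paths, Step 1 passes about 15% of the time. The rule finds a real mediator in about 4–9% of trials, against 11–35% without the Step 1 condition, and its positive results overstate the indirect effect by about 1.7–2.5 times.

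It would go too far to call the mediation analysis worthless: a positive verdict remains informative about whether a mediator exists, though not about its size. Because mediation is exploratory and no documented decision rests on it, this is a worthwhile and cheap improvement, not a threat to the pilot.

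**What to change.** In section 8.0, remove the requirement of a significant Step 1 and replace the three-part significance verdict with:

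> For each mediator and outcome we will report the indirect effect with a bootstrap or Monte Carlo 95% interval, whatever the Step 1 result, adjusted for baseline mediator and outcome where a baseline value exists in both arms. Results are exploratory, all pairs examined will be listed, and an interval that contains zero will not be read as absence of mediation.

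Then settle four details.
- **Mediators in Step 3.** State whether they enter singly or together.
- **Pairs.** Limit them to those with data in both arms. Table 2 implies up to 27 own-person pairs (3 mediators × 6 patient outcomes + 3 × 3 partner outcomes). Section 8.0 omits depression from its secondary list, which gives 3 × 5 + 3 × 2 = 21. Check retention, which comes from SSTAR data and has no natural baseline. Check phone-based sleep, since study phones are mailed after randomization and partners in the A-CHESS arm receive no software. Together these affect up to 9 pairs.
- **Risky drinking days.** Name the link function and report the indirect effect as a difference in mean days per 60 days from model predictions. Under an assumed log link, a product of coefficients of −0.35 is a ratio of exp(−0.35) = 0.705. That is 15 × 0.295 = 4.4 fewer days if the control mean is 15, but 5 × 0.295 = 1.5 if it is 5.
- **Editorial.** The plan writes "Step 3, the intervention variable and mediator variables will be regressed on the outcomes", which reverses outcome and predictors. Reword it as the outcomes regressed on the intervention and mediator variables. The intended model is clear from the conditions that follow.

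The cost is wording and some analysis code. Limited to those pairs, it needs no new data, since Table 2 schedules the mediators at 0, 2, 4 and 6 months. The downside is no yes/no answer and wide intervals: the median width is 0.90–0.97 SD with one follow-up in the cases above. With no mediator, 0.9–3.3% of these intervals exclude zero. Over 27 pairs that is up to about one by chance (27 × 0.033 = 0.9), which is why all pairs should be listed.

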and competence. Importantly, the patient effects of Partner- and A-CHESS will affect outcomes both directly (by affecting the patient's secondary outcomes) and by affecting the partner (and vice versa). For example, if PartnerCHESS boosts the partner's feelings of relatedness, the patient's feelings of relatedness may increase as a result.⁵⁹ PartnerCHESS effects on intrinsic motivation, competence, and relatedness will mediate its effects on secondary outcomes such as negative affect.⁶⁰ Because couple interventions can vary by gender,^{61,62} we anticipate that the sex of the patient and partner will moderate the indirect effects of PartnerCHESS on both mediators and secondary outcomes (i.e., women – partners or patients – will use discussion groups more and will benefit more). Similar expectations hold for patients assigned to A-CHESS, except that the partner will not be directly affected by A-CHESS since the partner does not have access to it. However, partners may be indirectly affected by the changes A-CHESS makes in patients. Finally, we anticipate that the extent to which partners PartnerCHESS will affect mediation and secondary outcomes.

Inclusion of sex as a moderator variable. We will examine how men and women use the interventions differently and how the interventions affect them differently.

Comparison group and TAU. Appropriate comparison groups are a hotly debated topic.⁶³⁻⁶⁹ We considered using TAU for this pilot test and a possible RCT, but our concerns about the lack of equipoise and the need for the comparison arm to offer some proven benefit (as A-CHESS does) led us to propose comparing PartnerCHESS+TAU to A-CHESS+TAU rather than comparing PartnerCHESS+TAU to TAU alone.

Treatment as Usual (TAU). At our recruitment site (SSTAR), TAU involves all patients learning core CBT skills. Patients receive training in anger and depression management, communication skills, distress tolerance, enjoying recovery, maintaining sobriety, parenting, problem solving, relapse prevention, seeking safety, and setting weekly objectives. A-CHESS and PartnerCHESS will prompt patients to use – and how to use – the skills that SSTAR teaches. SSTAR uses a fidelity scale to ensure that trainers teach the required skills, and we will use it to ensure that our services remind participants of the same skills.

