7.0 STUDY PARAMETERS

40 dyads will be recruited, 6 of whom will participate in development and initial testing of PartnerCHESS and the survey instruments. The remaining 34 dyads will be randomized on a 1:1 ratio to either A-CHESS + TAU or PartnerCHESS + TAU. Subjects will be stratified by gender and have access to A-CHESS or PartnerCHESS for 6 months.

Patients will have access to A-CHESS and Patients/Partners will have access to Partner CHESS for the 6 months of the study. They will be allowed to keep the phone, so that they could continue to use those interventions if they had other ways to access the two systems. Partners in the A-CHESS group will not have access to either app.

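### Interaction terms are judged by significance, with no list of mediator-by-moderator terms, no alpha and no multiplicity rule, in a pilot that disclaims power for outcomes

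*Combined protocol and SAP*

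**What the plan says.** All of this is in the combined protocol and SAP.

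- **Gender (8.0, Modeling mediation and moderation).** Two interactions are named: "We will test whether patient and partner gender moderates the effect of intervention on outcomes". Interaction terms go into the regression, and the plan will then "determine whether those terms significantly contribute to the outcome predictions that exist independent of other significant contributors".
- **Moderated mediation (same place).** "We will develop a moderated mediation structure to determine whether the results are best described by meaningful higher-order interaction terms based on mediator-moderator combinations". No such term is listed. The only illustration is that a mediator might act more strongly in one sex than in the other.
- **Mediation (same place).** Competence, intrinsic motivation and relatedness are examined in patients and in partners, against primary and secondary outcomes. A three-part criterion follows, opening "Mediator effects are statistically significant if". It is written for mediators and is not extended to interaction terms.
- **Moderators (8.0, Mediators and moderators).** Technology use is a second moderator besides gender.
- **Hypothesis (5.0, Conceptual model of study).** "we anticipate that the sex of the patient and partner will moderate the indirect effects of PartnerCHESS on both mediators and secondary outcomes". A parenthesis adds that women are expected to gain more.
- **Status (8.0).** The data analysis plan presents the conceptual model as something to explore. The power paragraph says the pilot has no power for outcome effects.
- **Size.** Section 7.0: "The remaining 34 dyads will be randomized on a 1:1 ratio". Section 5.0: "we expect a dropout rate of about 10%, leaving about 15 dyads per arm to complete the pilot RCT".

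No alpha, number of tests or multiplicity adjustment is stated anywhere.

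**The concern.** A significance criterion applied to an open list of terms yields verdicts whose error rate nobody can state. The plan does not require all fitted terms to be shown or their number to be given, so a reader of the results could not discount a lone significant interaction for the search behind it.

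The conclusion at risk is that some pathway works differently in women and men. Section 5.0 already predicts a direction, so a chance result that agrees with it would look like confirmation. Interactions are also estimated less precisely than the arm comparison, for which the plan itself disclaims power.

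**Working it through.** **1. Sample.** 34 dyads randomized 1:1 is 17 per arm. With 10% dropout, 17 × 0.90 = 15.3, which reproduces the plan's figure of about 15 per arm, or 30 dyads.

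**2. Counting terms.** Take patient gender only and one value per outcome. With K outcomes and M mediators there are K arm-by-gender terms on outcomes, M arm-by-gender terms on mediators and K × M mediator-by-gender terms.
- M is 3 (one person) or 6 (patient and partner).
- K is 2 for the primary outcomes and 5 when retention, negative affect and sleep are added for the patient (8.0).
- K is 6 with partner negative affect, and 8 with patient and partner depression, which Table 2 in section 6.0 lists as secondary.

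**3. One term at a time.** Two-sided 5% per test is an assumption. If tests were independent, the chance of at least one false positive is 1 − 0.95^m for m terms. The simulation removes the independence assumption: 30 dyads, equal arms, near-even gender split, no true arm, gender or interaction effect, and a common correlation of 0.2 to 0.8 among outcomes and mediators.

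| K | M | Terms m | If independent | Simulated |
|---|---|---|---|---|
| 2 | 3 | 2 + 3 + 6 = 11 | 43% | 33–44% |
| 5 | 3 | 5 + 3 + 15 = 23 | 69% | 50–68% |
| 6 | 6 | 6 + 6 + 36 = 48 | 91% | 74–95% (K = 6 and 8 together) |
| 8 | 6 | 8 + 6 + 48 = 62 | 96% | as above |

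The expected number of false positives is 0.05 × 48 = 2.4 to 0.05 × 62 = 3.1 in the last two rows.

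The arm-by-gender terms on outcomes alone, with both patient and partner gender and 5 outcomes (10 tests), give 22–34% in simulation. That assumes 10% same-sex couples and correlation 0 to 0.7. The two genders nearly mirror each other in opposite-sex couples, so this is below the independent value of 1 − 0.95^10 = 40%. On the fullest reading (both genders, 9 outcomes, 6 mediators, 126 terms) the simulated range for any term is 91–99%.

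**4. One joint test of all mediator-by-gender terms per outcome.** If independent, 1 − 0.95^5 = 23% and 1 − 0.95^8 = 34%. Simulated: 22–36% with 5–8 outcomes. For the two primary outcomes alone it is 8–11%.

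**5. Size of a significant interaction.** With 15 per arm split evenly by gender (7.5 per cell) and one value per outcome:
- SE = √(4 × 1/7.5) = 0.73 SD
- smallest significant interaction = t(0.975, 26 df) × SE = 2.06 × 0.73 = 1.50 SD
- power for an interaction of 0.35 SD is about 7.5%.

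Averaging three follow-ups with baseline adjustment, at an assumed correlation r of 0.3 to 0.7, multiplies the variance by (1 + 2r)/3 − r², which is 0.44 at r = 0.3 and 0.31 at r = 0.7. The SE becomes 0.49 to 0.41 SD and the threshold 1.0 to 0.84 SD. Power at 0.35 SD is still only 11–13%.

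**The case against.** **The plan is an exploratory pilot that claims no power.** This lowers the stakes. It does not remove the significance criterion or require that every term be shown.

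**The error rate depends on a procedure the plan does not spell out.** This stands, and it is why the result is a range. Asking which structure best describes the results can be read as a model comparison, which is the joint-test case. If moderated mediation were examined only where the first mediation criteria had been met, the rate for those terms would fall to 0–2.5%. That gate is not written for interaction terms, and it would not cover the arm-by-gender tests.

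**The precision argument ignores repeated measures.** This is partly right. The 1.5 SD threshold is for a single value per outcome and falls to about 0.84–1.0 SD under the assumptions above. Nor is d = .35 a benchmark for interactions: the plan adopts it to size the later trial.

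A reader might also infer several stronger points that the documents do not support:
- *No interaction is named.* Intervention by patient gender and by partner gender are named. Only the mediator-by-moderator terms are not.
- *Every outcome is searched.* Mediation is limited to primary and secondary outcomes.
- *Significant terms are retained in the model.* No retention step is written.
- *Any significant interaction must be a gross overestimate.* That holds only if the true interaction is small.
- *The later trial's moderators or target group will be chosen on pilot p-values.* Nothing says so. The R01 is to rest on a fixed effect size, earlier work and feasibility lessons.

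**Conclusion.** The point holds as a cheap improvement to the plan. Interaction terms are judged by significance or by which structure fits best, the mediator-by-moderator terms are open-ended, and no alpha or multiplicity rule exists.

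At an assumed two-sided 5%, with terms tested one at a time under the null, the chance of at least one false positive is about 33–95%. It is about 74–95% with 6 mediators and 6–8 outcomes. With a joint test per outcome it is about 22–36% for 5–8 outcomes, still well above 5%. These figures rest on patient gender only and one value per outcome. Testing separate time points or technology use as well would add terms.

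It would be tempting to say that a false moderated finding is close to certain. Only the fullest count of terms supports that. Nor do 30 dyads raise the false-positive rate of a valid test: the small sample lowers power and makes chance findings large.

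**What to change.** In section 8.0, Modeling mediation and moderation:

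1. Replace the significance and best-description criteria for interaction terms with estimates and 95% CIs.
2. Report every gender and mediator-by-gender term fitted in one table, with the number of terms examined, labelled hypothesis-generating.
3. State that no moderation conclusion will be drawn because a pilot interaction reached p<0.05.

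Naming one lead contrast is optional. If one is named, it should follow the plan's own hypothesis in section 5.0, which concerns sex moderating indirect effects on mediators and secondary outcomes.

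The cost is wording only, with no new data or participants. The downside is that the pilot can no longer report a significant gender-specific pathway.
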